4.4 Duration of Study Participation

For each subject, the study intervention phase will vary as this phase will depend on the duration of each individual inpatient admission. The follow up time period will extend to 90 days after discharge for all patients.

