5.1 Description

The Attending Nurse will meet patients and their families within the first 24 hours of their admission to begin the integrated care process and follow them until discharge. If assigned to the attending nurse model, patients will be followed by her if they are transferred to another service or unit rather than drop out of the study. The attending nurse will record the tasks she completes with each patient and the time each task required. This record will then become a part of the patient's medical record.

The Attending Nurse will have, in addition to a BSN and RN, at least 5 years of experience managing stroke and other neuroscience patients at the Hospital of the University of Pennsylvania. Additionally, she will also have training specific to the role of attending nurse through mentorship by nurses who currently work in this role at our institutions and at other institutions.

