5.2 Intervention Regimen

The attending nurse will spend 30 minutes to 45 minutes upon initial evaluation to determine the patients' goals, barriers, and needs. The amount of time spent with each subject following the initial visit will vary based on the patient. To limit the demands on the attending nurse, she will never carry a case load of more than 8 patients at a single time. If on an even-numbered weekday the attending nurse has 8 patients, than the subject will be assigned to the routine care arm of the trial. Patients who are assigned to the attending nurse model of care will be seen by that nurse on a daily (weekday) basis in addition to being cared for by their regular care team of physicians and rotating staff nurses. All staff nurses as well

as the attending nurse will participate in morning interdisciplinary table rounds in keeping with preexistent quality processes.

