7.5 Subject Population(s) for Analysis

The entire subject population who undergo treatment assignment will be studied primarily via intention to treat analysis comparing data from follow up phone calls between groups. An as-treated analysis will also be performed.

Analysis will be performed on some pre-defined subgroups where we may expect to see effect modification: major stroke vs. minor strokes (NIHSS \leq 5), multiple medications vs. few medications, patients who were admitted following a recurrent stroke vs. a new stroke, and hemorrhagic stroke vs. ischemic stroke subtypes.

8 Safety and Adverse Events

This protocol is extremely low risk as it assigns patients to already existent forms of inpatient care. This study does not include any experimental treatment. Given there is no proposed intervention or proposed management beyond two existing forms of standard clinical care, the routine collection of adverse events is not relevant, as those will be part of routine care. However, there may be a difference between the two arms in terms of specific events of interest. These specific events of interest include falls, aspiration pneumonia, and subsequent (post-discharge) major cardiovascular and cerebrovascular events (MACCE) including stroke (ischemic, hemorrhagic, or unknown), myocardial infarction, and death of any cause. Transfers to a higher level of care (e.g. to the Neuro ICU or medical ICU from the floor) that occur as part of routine care will also be considered events of interest. We will also report any unanticipated events.

All of the aforementioned events of particular interest will be assessed while the subject is in the hospital in keeping with standard clinical care. During follow up phone calls, the interviewee will ask patients and/or their family members specifically about the occurrence of MACCEs including and death of any cause.

The safety of each mode of nursing care while the subject is in-house will be tracked using the quality control processes that are already in place as part of standard inpatient care.

9 Study Administration, Data Handling and Record Keeping

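### The secondary as-treated analysis groups patients by receipt of the attending nurse, which is settled after the admission date, and names no adjustment; the caseload rule can carry the same problem into intention to treat

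*Combined protocol and SAP*

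**What the plan says.** Section 7.5 states that everyone who undergoes assignment "will be studied primarily via intention to treat analysis", and then that "An as-treated analysis will also be performed". It does not say what counts as treated, which test is used, whether anything is adjusted for, or how the result will be weighed. Section 7.4 offers only Student t-tests and the Pearson chi-square test.

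Four passages bear on who receives the nurse:

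- **Caseload (5.2):** "she will never carry a case load of more than 8 patients at a single time". When she is full, an even-day patient is not described as missed: "the subject will be assigned to the routine care arm of the trial".
- **First contact (5.1):** "The Attending Nurse will meet patients and their families within the first 24 hours of their admission".
- **Later contact (5.2):** patients "will be seen by that nurse on a daily (weekday) basis".
- **Length of exposure (4.4):** "this phase will depend on the duration of each individual inpatient admission".

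Receipt can be measured, because section 5.1 says that "The attending nurse will record the tasks she completes with each patient and the time each task required". Section 3.1.2 says that routine-care patients will have no contact with her.

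**The concern.** Allocation by admission date is the plan's only claimed source of comparable groups (section 3.1). On the usual meaning of as-treated, an even-day patient whom the nurse never saw is counted with the controls. The groups are then formed partly by events after admission, and nothing in the plan corrects for that. If unseen patients would have adhered worse anyway, the nurse looks better than she is. If they would have adhered better, a benefit is hidden or reversed.

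This is the plan's only analysis of the effect of actually receiving the nurse, so a difference from the intention-to-treat result could be read as an effect of exposure when it is only patient mix.

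The caseload rule raises a second question. If overflow patients are assigned to routine care, they are controls under intention to treat as well, although they were admitted on an even day.

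**Working it through.** The plan gives no figure for non-receipt or for how unseen patients differ, so there is nothing of its own to reproduce. The check asks how large the bias could be.

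**Inputs from the plan:** 65% control adherence and 186 patients per arm (section 7.3); 700-800 stroke admissions a year (section 4.5).

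**Assumptions:** no true effect; a share u of even-day patients unseen, 10% to 25%; adherence in unseen patients lower than in seen patients by g, 5 to 15 points.

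**Bias.** Let m be the common mean.

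- Even-day mean: m = (1-u)s + u(s-g), so seen patients have s = m + ug and unseen patients have m - (1-u)g.
- As-treated controls pool the odd-day patients with the unseen: [m + u(m - (1-u)g)]/(1+u) = m - u(1-u)g/(1+u).
- False difference: ug + u(1-u)g/(1+u) = 2ug/(1+u).

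Reversing the sign of g reverses the sign of the bias. The same formula serves the SPER, with g in points.

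**False-positive rate.** The groups have 186(1-u) and 186(1+u) patients. The standard error (SE) is approximately √{0.65 × 0.35 × [1/(186(1-u)) + 1/(186(1+u))]}. For u = 15% the groups are 158.1 and 213.9, which gives an SE of about 5.0 points. The bias is then 2.6/5.0 ≈ 0.52 SE, and the two-sided 5% test rejects in about 8% of trials.

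| u | g (points) | Bias = 2ug/(1+u) | Bias (points) | False positives |
|---|---|---|---|---|
| 10% | 5 | 0.010/1.10 | 0.9 | about 5% |
| 15% | 10 | 0.030/1.15 | 2.6 | about 8% |
| 25% | 15 | 0.075/1.25 | 6.0 | about 22% |

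With no prognostic gap there is no bias: simulated at u = 20% and g = 0, the as-treated test rejected in 4.9% of trials. Grouping by date allocation stayed near 5% in every simulated case.

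**How often the cap might bind.** Length of stay is not given, so a mean is assumed. Half of the admissions fall on even days. The average load is (admissions/365) × 0.5 × mean stay, for example 700/365 × 0.5 × 4 = 3.84 patients. The Erlang loss formula with 8 places gives the share of even-day patients who find the nurse full:

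| Mean stay (assumed) | All admissions count | Weekday admissions only (load × 5/7) |
|---|---|---|
| 4 days | 3-4% | 0.5-1% |
| 6 days | 11-15% | 3-6% |
| 8 days | 22-28% | 9-14% |

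**Which analysis the cap affects.** Read literally, section 5.2 makes overflow patients controls by assignment. The as-treated analysis then moves none of them, and intention to treat by assigned arm already contains the shift. If intention to treat follows the admission date, they stay in the even-day group and only the as-treated analysis moves them. Section 7.5 does not say which is meant.

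**The case against.** The strongest reply is that little depends on this analysis. Intention to treat is primary and as-treated is one added sentence. At the central assumptions the bias is about half a standard error. That stands, and it limits the point to a modest improvement.

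A reader might infer that patients with TIA or minor stroke, or those admitted out of hours, are the ones who go unseen, and that they differ in knowledge and adherence. No passage says so. Section 5.1 promises a first meeting within 24 hours and continued contact after transfer, and section 3.1.3 has the nurse told of every even-day admission. On paper, non-receipt other than overflow is a deviation of unknown frequency. Section 4.4 says only that exposure varies with stay. A link between busy periods and prognosis is weaker still.

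A reader might also expect much higher error rates. These arise only with larger assumed gaps: about 26% at u = 20% with a 20-point gap, and 77% at u = 30% with a 30-point gap. Nothing in the documents supports gaps of that size.

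Two further replies have some force. The plan compares stroke severity and medical history between groups (section 7.4.1) and has a major versus minor stroke subgroup (section 7.5), so an imbalance might be noticed; noticing is not adjusting. Defining treated, labelling the analysis exploratory and adjusting for severity and diagnosis would also help, but would handle only measured differences.

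**Conclusion.** The point holds as a limited one. Run with the tests the plan names, the as-treated analysis gives up the comparison by admission date and puts nothing in its place. The bias is 0.9 to 6.0 points over the assumed range, in either direction, and 2.6 points centrally, with a false-positive rate of about 8% rather than 5%. All of this is conditional on missed contact being related to prognosis. The documents give neither the unseen share nor the gap.

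It would be wrong to conclude that the trial's main result is compromised by the as-treated analysis. The route by which the primary analysis could be affected is the overflow rule in section 5.2, and only if intention to treat is defined by assigned arm and overflow is related to outcome.

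**What to change.** 1. In section 7.5, define the intention-to-treat groups by admission-date parity as allocated, and keep even-day overflow patients in the even-day group for analysis. This changes the analysis wording only, not who is cared for by the nurse.
2. State which admissions count as even or odd weekdays. Section 3.1 refers both to the day of the week and to even-numbered weekdays, and weekend admissions have no stated arm.
3. Replace the unadjusted as-treated comparison with a complier-average estimate, labelled secondary: the outcome difference by parity divided by the difference by parity in the proportion seen. Fit it by two-stage least squares with date-clustered standard errors. Define receipt as any contact in the attending-nurse record.

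**Cost.** This needs SAP wording and one model. Dates of stay are already abstracted (section 9.2) and contacts are already logged (section 5.1). Because the log enters the medical record and the interviewer who abstracts the chart is to be blinded (section 5.3), someone else should extract receipt.

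The interval is about 18% wider than the intention-to-treat interval if 85% of even-day patients and no odd-day patients are seen (1/0.85 = 1.18), before any effect of clustering. At 90% and 75% seen it is about 11% and 33% wider (1/0.90 and 1/0.75). The estimate assumes that date parity affects outcome only through the nurse. It does not deal with patients who cannot be reached by telephone.

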9.1 Confidentiality

Information about study patients will be kept confidential and managed according to the requirements of the Health Insurance Portability and Accountability Act of 1996 (HIPAA).

9.2 Data Collection and Management

Data will be abstracted regarding demographics, medical/surgical history, stroke location, and dates of hospital stay. The results of follow-up phone calls will be recorded by the interviewer and directly inputted into the RedCap database. The database will be kept in RedCap prior to data cleaning. Hard copies of survey results will be kept in locked file cabinets.

Data will be managed and stored using REDCap, the software toolset and workflow methodology for electronic collection and management of research data, developed specifically around HIPAA-Security guidelines. REDCap (Research Electronic Data Capture) is a secure, web-based application that is flexible enough to be used for a variety of types of research. REDCap provides an intuitive user interface that streamlines project development and improves data entry through real-time validation rules (with automated data type and range checks). REDCap also provides easy data manipulation (with audit trails for reporting, monitoring and querying patient records) and an automated export mechanism to common statistical packages (SPSS, SAS, Stata, R/S-Plus). In addition to traditional data capture functionality, REDCap's survey capabilities are a powerful tool for building and managing online surveys. The research team can create and design surveys in a web browser and engage potential respondents using a variety of notification methods. All data collection projects rely on a thorough, study-specific data dictionary, defined by all members of the research team in an iterative, self-documenting process. This iterative development and testing process results in a well-planned and individualized data collection strategy.

The REDCap MySQL database is replicated in real time to a completely redundant instance of MySQL. The redundant instance is available for restoration of the primary database or for manual failover in the case of primary database failure. Time-stamped backup files are made from the replicated database daily by HUP Research Information Systems using automated backup routines.

Data and backups are stored in the HUP Research Information Systems Storage Area Network (SAN). Access to the SAN directories where data are stored will be limited to Research Information Systems personnel, with authentication performed using HUP's enterprise Active Directory service. De-identified data will be analyzed using STATA or SPSS.

The data that is collected will have a unique code assigned by the investigator when it is acquired to code each subject at the time of data harvesting to ensure duplicate data is not collected and PHI is protected. This unique case number will not be possible to link to any other information pertaining to each subject. By doing this, the patients' privacy will be protected. Patients' names and medical record numbers will be coded and kept separately from the database in a password protected file. The PI will ensure that data is coded correctly so that PHI is protected.

All data will be maintained on a password protected computerized database on a computer that will have a protected login. No data in the database will contain PHI as each subject will have been assigned a unique code at the time of data acquisition. The coded identifiers list will be stored in a password protected file separate from the main database in a computer that requires a unique university ID to access.

Only the PIs and the clinical research team will have access to the database. Only the PIs will have access to the coded identifier list so as to minimize the risk of a confidentiality breach. Confidentiality of the data will be ensured for as long as it is kept.

9.3 *Records Retention*

Any patient data will be held only until data analysis is complete. Once data is no longer needed for research, it will be electronically destroyed in a way that leaves no trace. Both the coded-identifiers list as well as the data set will be destroyed.

10 Study Monitoring, Auditing, and Inspecting

10.1 *Study Monitoring Plan*

Results of follow up phone calls will be discussed with the PIs on a weekly basis. The PI will review all data that is collected via REDCap. Data will be collected over the course of 6 months, cleaned for a month and analyzed for another month. The Investigator will also ensure that the monitor or other compliance or quality assurance reviewer is given access to all the above noted study-related documents and has adequate space to conduct the monitoring visit.

10.2 *Auditing and Inspecting*

The investigator will permit study-related monitoring, audits, and inspections by the EC/IRB, the sponsor, government regulatory bodies, and University compliance and quality assurance groups of all study related documents (e.g. source documents, regulatory documents, data collection instruments, study data etc.). The investigator will ensure the capability for inspections of applicable study-related facilities.

Participation as an investigator in this study implies acceptance of potential inspection by government regulatory authorities and applicable University compliance and quality assurance offices.

11 Ethical Considerations

This study is to be conducted in accordance with applicable US government regulations and international standards of Good Clinical Practice, and applicable institutional research policies and procedures.

This protocol and any amendments will be submitted to a properly constituted independent Ethics Committee (EC) or Institutional Review Board (IRB), in agreement with local legal prescriptions, for formal approval of the study conduct. The decision of the EC/IRB concerning the conduct of the study will be made in writing to the investigator and a copy of this decision will be provided to the sponsor before commencement of this study.

11.1 *Risks*

The major risk of this study is a breach in PHI. Data will be protected as detailed above to avoid the damaging effects of a PHI breach. If patients or their family find follow up interview questionnaires too burdensome or psychologically straining during phone interviews, they can simply stop answering them.

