Our central hypothesis is that the attending nurse will enhance critical patient-centered elements of care that will in turn improve patient education and shared decision-making, medication adherence, stroke-related health literacy, and reduce early readmissions to ultimately yield improved patient quality of life. Our primary objective is to determine whether the attending nurse model of care improves stroke patients' health at 7 days, 30 days, and 90 days after hospital discharge as assessed through questionnaires.

**Number of
Patients**

372 patients

Main Inclusion and Exclusion Criteria	
We will include all adult patients admitted to the Vascular Neurology Service with a clinical diagnosis of stroke, brain hemorrhage, or transient ischemic attack.
 
We will exclude patients whose level of care is limited to comfort care or hospice, those with severe dementia prior to admission, and those who are both non-communicative and have no family or other social support.

Investigational Product	
None
 
This is a comparative effectiveness study comparing two models of nursing care delivery to stroke patients (attending nurse model vs. conventional inpatient nursing care)

Duration of administration (if applicable)	
The duration of the intervention phase will depend on the duration of a patient's hospital admission.

Reference therapy	
The reference therapy is standard inpatient nursing care.

Statistical Methodology	
Our primary outcome will be scores on scales of medication adherence and stroke education retention. The scores on these tests will be compared between patients who were assigned to the attending nurse model of care versus standard nursing care.
 
Secondary outcomes will include comparisons between groups of the thirty day readmission rate, scores on a patient-centered stroke impact scale, 2 modified quality of life scales, results of a newly designed series of 13 Likert style questions, and a global statistic that includes the results of all scales.

Safety Evaluations	
All enrolled patients will be evaluated via telephone interview at 7, 30, and 90 days following hospital discharge and screened for major cardiovascular and cerebrovascular events. While in the hospital, subject safety will be assured via already existent quality assurance mechanisms.

Data and Safety Monitoring Plan	
The PIs will be responsible for monitoring the data quality and the ongoing safety of patients.

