3.2 Study Endpoints

3.2.1 Primary Study Endpoints

- Primary endpoints will be stroke education retention as measured by the SPER and medication adherence as measured by MMAS-4 as these are the areas where we anticipate the largest potential effect of the nurse attending. The mean scores on these two tests will be compared between groups at each time interval that they are administered.

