5.3 Blinding

The 7, 30, and 90 phone surveys will be blinded to patients' group assignment. Staff nurses will not be blinded as to which patient the attending nurse is caring for. The PIs will not be blinded to subject treatment assignment as they will need to assure subject assignment is preformed correctly. Patients will not be formally blinded to their arm assignment, though patients may not realize that alternative models of care exist on the Vascular Neurology service. Waiving consent upon admission will help maintain patients' blinding. During the first follow up phone call, as part of the consenting process, we will specify that we are comparing different nursing styles of care. The interviewer preforming follow up phone calls and collecting data from the patient electronic medical record will be blinded to study group assignment.

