6.3 Follow Up Phase of the Study

Follow-up visits will be conducted by telephone only. Informed consent for phone interviews will be obtained prior to the interview. Consent will also be obtained for data collection from the patients Hospital of the University of Pennsylvania electronic medical record. Whether the patient, a family member, or other person is answering the pertinent survey questions will be recorded. Patients may become fatigued when answering the survey questions in which case they can simply ask to stop and the phone conversation will end.

6.3.1 7 days following discharge

At 7 days after hospital discharge, the MMAS-4, SPER, the exploratory 13 Likert-style questions and two modified overall health questions will be administered. There are no well validated surveys regarding the inpatient experience that are patient centered and stroke specific so we designed 13 questions which focus on subject's perception of their inpatient stay as well questions designed to assess quality of life following stroke. The newly devised Likert-style questions as well as the 2 modified overall quality of health questions have been reviewed by a stroke-survivor in her role as patient advocate who was cared for at our institution. The single health literacy question will also be repeated at the 7 day follow up visit and interviewees will be asked about readmission. Though ideally patients will answer all survey questions themselves, responses to survey questions will be accepted from a legal representative provided they can answer accurately. Each interviewee will be identified based on their relationship to the patient on survey collection forms.

6.3.2 30 days following discharge

At 30 days following hospital discharge, the SIS and the MMAS-4 will be administered. Inquiry as to whether or not the patient has been readmitted will occur.

6.3.3 90 days following discharge

At 90 days following hospital discharge, the MMAS-4, SPER, the exploratory 13 Likert-style questions and the 2 modified global quality of health questions will be administered again. Patients will also be asked about any readmissions.

6.4 *Unscheduled Visits*

Clinic visits and other unscheduled visits will not replace phone interviews and will be entirely separate from this study.

6.5 *Subject Withdrawal*

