Patients may withdraw from the study at any time without impact to their care. Patients may also be discontinued from the study at the discretion of the PIs for lack of adherence to intervention or study procedures or difficulty obtaining follow up or unexpected events. The PI may also withdraw patients who violate the study plan, or to protect the subject for reasons of safety or for administrative reasons. It will be documented whether or not each subject completes the study.

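### PIs who know each patient's arm and can discontinue patients review primary-outcome results weekly, with no limit or masking stated

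*Combined protocol and SAP*

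**What the plan says.** Section 10.1 (Study Monitoring Plan) sets the routine: "Results of follow up phone calls will be discussed with the PIs on a weekly basis". It adds: "The PI will review all data that is collected via REDCap". Neither sentence says which call items are meant, or whether arm is masked.

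Section 5.3 (Blinding) states the PIs' position and gives one reason for it: "The PIs will not be blinded to subject treatment assignment as they will need to assure subject assignment is preformed correctly". The Study Summary assigns them the monitoring role: "The PIs will be responsible for monitoring the data quality and the ongoing safety of patients". Section 6.5 (Subject Withdrawal) gives them a discretionary power: "Patients may also be discontinued from the study at the discretion of the PIs for lack of adherence to intervention or study procedures". The same section extends that power to trouble in obtaining follow-up, unexpected events, violations of the plan, patient safety and administrative reasons.

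The person who makes the calls and abstracts the chart is to be blinded (3.1 and 5.3). No interim analysis or stopping rule is given. A data monitoring committee appears only in the abbreviation list.

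**The concern.** The stated reason for unblinding the PIs, checking assignment, needs the admission date and the arm. It does not need outcome scores. Monitoring of data quality and safety needs call completion, missing or implausible entries, and reported events. It does not need SPER or MMAS-4 scores in the hands of people who know the arm. The plan nevertheless gives the same people both the arm and the scores, during the trial, and attaches no decision to the review that would justify it.

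At stake is the independence of later decisions from outcomes already seen. A discontinuation after the first call can remove a patient's day-90 result. A conversation about results can also reach the interviewer, whose blinding is the main protection of outcome assessment in this trial. Neither exposure can be undone afterwards.

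**Working it through.** No figure in the plan bears on this point, so the check sets the sections side by side.

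1. **Do the calls contain the primary outcomes?** Section 3.2.1: "Primary endpoints will be stroke education retention as measured by the SPER and medication adherence as measured by MMAS-4". Section 6.3.1: "At 7 days after hospital discharge, the MMAS-4, SPER, the exploratory 13 Likert-style questions and two modified overall health questions will be administered". Table 1 and sections 6.3.1 to 6.3.3 place MMAS-4 at 7, 30 and 90 days and SPER at 7 and 90 days. Call results and the REDCap data, read plainly, therefore include both.

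2. **Can the PIs link a score to an arm?** Yes. They are unblinded under 5.3, and section 9.2 says: "Only the PIs will have access to the coded identifier list". The admission date gives a second route. Dates of stay are abstracted (9.2), and arm follows odd or even admission date (3.1.3), except when the nurse already has 8 patients (5.2). Storing arm in a separate file would therefore not hide it.

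3. **Does anything limit what they see?** The Study Summary, 5.3, 5.4, 7.4, 8, 9.2, 10.1 and 10.2 contain no restriction to events or completeness, no pooling and no masking by arm. No independent reviewer of outcomes is described.

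4. **Which later decisions could be affected?**
   - *Discontinuation (6.5).* Difficulty with follow-up is a listed reason and can arise only after discharge, so the power extends into the follow-up period. Section 7.1 places the primary comparison at 7 and 90 days. The nominal gap is 90 − 7 = 83 days. With the windows in Table 1 (±3 and ±14 days) it runs from (90 − 14) − (7 + 3) = 66 days to (90 + 14) − (7 − 3) = 100 days. Throughout that gap a day-7 score can be known while the day-90 score is still to come.
   - *Interviewing and SPER scoring.* Section 7.1 grades SPER questions 1 and 2 as 0, 1 or 2 according to how complete the answer is, which takes judgement. They carry 2 × 2 = 4 of the 2 × 5 = 10 points. This route opens only if the interviewer takes part in the weekly discussion, which the documents do not address.
   - *Assignment.* The date rule and the caseload limit leave little room here.

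5. **Can the effect be sized?** No. That would need the number of discontinuations decided with scores in view and their relation to outcome, and the documents give neither.

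**The case against.** The best defence is practical. This is an unfunded, single-centre study whose PIs are responsible for data quality, and case-level review can catch scoring and entry errors without any formal decision rule. The word for what is discussed may mean only completion and events. Assignment follows the calendar, an admitting physician judges eligibility (3.1.1), a blinded interviewer makes the calls within fixed windows, and the primary analysis is by intention to treat (7.5).

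Much of this stands, and it narrows the point to discontinuation and the interviewer. It does not remove the point. Intention to treat keeps a patient in the assigned arm but cannot supply a day-90 score that was never collected, and 6.5.1 does not say whether patients discontinued by a PI are still called. A narrow reading of the weekly discussion does not help either, because the next part of 10.1 covers all REDCap data.

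A reader might infer more than the documents support:
- *That the weekly discussion is the trial's safety oversight.* In-hospital safety runs through existing quality processes (Study Summary, 7.4.3, 8), and audits by the IRB, sponsor and compliance bodies are allowed (10.2).
- *That the PIs follow the outcomes by arm.* No section says results are tabulated or compared by arm. Only access is shown.
- *That weekly meetings over six months amount to some 26 interim looks with inflated type I error.* That counts meetings. No test or stopping decision is attached to them.
- *That 11.4.1.1 is contradicted.* Its remark on blinding concerns what patients and families know of their care and supports the consent waiver. Section 5.3 openly leaves the PIs unblinded.
- *That the PIs could suppress an unfavourable result.* Section 13 says publication does not depend on the result.

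**Conclusion.** The point holds as one of access and missing separation: arm-aware PIs with discretion to discontinue patients receive primary-outcome results during the trial, with nothing to limit or mask them. It does not show that comparisons by arm are made or that any decision has been biased. The size and direction of any bias cannot be derived; the 83-day nominal gap describes how long the opportunity lasts, not its effect.

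The conclusion rests on two readings: that call results and all REDCap data include the scale scores, and that 6.5 applies after discharge. The interviewer route rests on a further assumption, attendance at the meetings, which the documents leave open. The change is worth making before enrolment because it is cheap and the exposure cannot be reversed.

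**What to change.** - **10.1, meeting content.** Limit the weekly meeting to call completion, missing or out-of-range data, and MACCE, readmission or unanticipated events.
- **10.1 and 9.2, scores.** Withhold SPER, MMAS-4 and other scale scores from anyone who knows assignment until the last day-90 call is done and the data are cleaned. Do this through REDCap user rights, and cover the hard copies that 9.2 keeps in locked cabinets.
- **Score-level checks.** Give these to the blinded survey staff already in the plan (5.4) and to the REDCap validation rules (9.2). State that arm is not discussed with the interviewer. Because 5.3 has the interviewer abstract the chart as well, use forms without dates of stay for these checks.
- **6.5.** State that PI discontinuation decisions are made and documented without sight of scores. The listed reasons need not change for this purpose.

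The cost is protocol wording, a permission setting and control of the paper forms, with some checking time moved to existing staff. The drawback is that the PIs cannot review scores themselves until cleaning is complete.
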